7.1 Discontinuation of Study Intervention

In some circumstances, it may be necessary for a participant to permanently discontinue (definitive discontinuation) study intervention. If study intervention is definitively discontinued, the participant will remain in the study to be evaluated for disease progression and/or OS. See the SoA (Section 1.3.1) for data to be collected at the time of withdrawal of study intervention, in follow-up, and for any further evaluations that need to be completed.

The study interventions may be interrupted for situations other than treatment-related AEs such as medical / surgical events or logistical reasons not related to study therapy. Participants should be placed back on study therapy within 3 weeks of the scheduled interruption, unless otherwise discussed with the sponsor. The reason for interruption should be documented in the participant's study record

7.1.1 Withdrawal Criteria

7.1.1.1 Withdrawal from Study Intervention Period

Participants MUST be withdrawn from the study intervention if any of the following occurs:

- At their own request or at the request of their legally acceptable representative (if acceptable by local law). At any time during the study and without giving reasons, a participant may decline to participate further. The participant will not suffer any disadvantage as a result.
- If, in the investigator's opinion, continuation of the study intervention would be harmful to the participant's well-being.
- Progressive disease as per RECIST 1.1; however, treatment beyond radiological progression per iRECIST is possible if the participant is still benefiting from treatment.
- Clinical progression (every effort should be made to obtain radiological confirmation of disease progression [PD] during active follow-up). Note: In cases where radiographic evaluation is not possible, clinical progression may be used. Clinical progression is based on the judgment of the investigator (e.g., defined as worsening of the ECOG PS ≥3 or symptomatic deterioration including increase in liver function tests).
- The development of a second primary malignancy that requires a different treatment.
- Development of any intercurrent illness or situation which may, in the judgment of the investigator, affect assessments of clinical status and study endpoints to a relevant degree.
- Severe allergic reactions, such as exfoliate erythroderma, anaphylaxis, or vascular collapse.
- Start of a new anti-cancer therapy.

Page 77 of 141

- Use of illicit drugs or other substances that may, in the opinion of the investigator or their designated associate(s), have a reasonable chance of contributing to toxicity or otherwise confound the results.
- Pregnancy.
- Participant lost to follow-up.
- Death.

Participants MAY be withdrawn from the study intervention for the following reasons:

- At the specific request of the sponsor and in liaison with the investigator (e.g. obvious non-compliance, safety concerns).
- Participants should be taken off study intervention for disease progression. However,
 if a participant has radiographic progression but is achieving a clinically meaningful
 benefit, an exception to continue study intervention may be considered following
 consultation with the sponsor.
 - o If the investigator considers radiographic changes secondary to drug-induced inflammation and not to tumor progression (i.e. in case of suspected pseudoprogression), the investigator may postpone a diagnosis of progressive disease until the next radiographic evaluation in the study, as per the criteria outlined in Appendix 10.5 in Section 10.5.3.
- Withdrawal of study intervention for abnormal liver function should be considered by the investigator when a participant meets one of the conditions outlined in Table 6–3 or if the investigator believes that it is in best interest of the participant.
- If a clinically significant electrocardiogram (ECG) finding is identified (including, but not limited to changes from baseline in QT interval corrected using Fridericia's formula [QTcF]) after enrollment, the investigator or qualified designee will determine if the participant can continue in the study and if any change in participant management is needed. This review of the ECG printed at the time of collection must be documented. Any new clinically relevant finding should be reported as an AE.

See the SoA (Section 1.3.1) for data to be collected at the time of intervention permanent discontinuation and follow-up and for any further evaluations that need to be completed.

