4.1.1.2 Intervention Period

The start of the intervention period is defined by the first administration of the combination study intervention.

Participants will be treated with 400 mg pembrolizumab IV Q6W.

Regorafenib will be given orally (p.o.) at a starting dose of 90 mg QD for 3 weeks of every 4 weeks (i.e., 3 weeks on, 1 week off). If the starting dose of 90 mg daily is well tolerated (absence of any grade rash/hand-foot skin reaction [HFSR] or other Grade 2 or higher clinically significant toxicity), the dose can be escalated to 120 mg daily any time after the first cycle of regorafenib, starting with W5D1. Dose modification guidelines for dose reduction in case of toxicity are detailed in Section 6.6.

To support participants in establishing the drug intake rhythm (i.e. 6-week cycle for pembrolizumab, 4-week cycle for regorafenib), the site personnel are asked to call participants regularly for at least the first 3 regorafenib treatment cycles to remind them of omitting regorafenib during the 4th week of a cycle.

Participants will continue to receive study intervention until disease progression as defined by RECIST 1.1, unacceptable toxicity, consent withdrawal, withdrawal from the study at the discretion of the investigator or his/her designated associate(s), or until any other withdrawal criteria are met. Treatment beyond radiological progression is possible if the participant is still benefiting from treatment (see Section 6).

Participants who complete 18 infusions of pembrolizumab need to discontinue treatment with pembrolizumab. Regorafenib treatment can be continued beyond 2 years until withdrawal criteria are met. Treatment with individual drugs (regorafenib or pembrolizumab) may continue on schedule even if the other drug is interrupted or permanently discontinued due to toxicity.

During the study, participants will undergo evaluations for safety, efficacy, PK, and tissue and blood/plasma for biomarker will be collected. See the SoA in Section 1.3 for the assessments during the intervention period.

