G2	 1st occurrence: Consider decrease by 1 dose level and institute supportive measures immediately^a. If no improvement, interrupt for ≥ 7 days, until toxicity resolves or improves to G1 No improvement ≤ 7 days or 2nd occurrence: Interrupt until toxicity resolves or improves to G1. When resuming treatment, treat at reduced dose level^a. 3rd occurrence: Discontinue 	No modification
G3	 1st occurrence: Institute supportive measures immediately. Interrupt therapy for ≥ 7 days until toxicity resolves or improves to G1. When resuming treatment, decrease by 1 dose level^a. 2nd occurrence: Institute supportive measures immediately. Interrupt therapy for ≥ 7 days until toxicity resolves or improves to G1. When resuming treatment, decrease by 1 additional dose level^a. 3rd occurrence: Discontinue 	No modification
	skin and subcutaneous disorders other than HFSR (includes rash, rash	
rash macular, rash ma	culopapular, rash papular, rash pruritic, exfoliative rash, pruritus, ecze	ma, dermatitis)
G2	No modifications	 Consider withholding for persistent symptoms Restart at same dose if resolution to ≤ G1 or baseline ≤ 12 weeks of last infusion Consider discontinuation if NO resolution ≤ 12 weeks of last infusion^b

Table 6-3: Dose Modification Guidance, Non-immune Toxicities

Event	Regorafenib	Pembrolizumab
G3	 Hold until recovery to ≤ G2 and restart at same dose level or reduce 1 dose level^a (at the investigator's discretion) 1st + 2nd re-appearance: Hold until recovery to ≤ G2 and reduce 1 dose level^a (at the investigator's discretion) 3rd re-appearance: Discontinue 	 Hold and restart at same dose if resolution to ≤ G1 or baseline ≤ 12 weeks of last infusion Hold and discontinue if NO resolution ≤ 12 weeks of last infusion^b
G4 (when applicable)	 Hold until recovery to ≤ G2 and reduce 1 dose level^a 1st re-appearance: Hold until recovery to ≤ G2 and reduce 1 additional dose level^a 2nd re-appearance: Discontinue 	Discontinue ^b
Specific guidance for HYPER	rension	
G1	 No change. Consider increased BP monitoring 	No modification
G2	 If symptomatic, hold until symptoms resolve AND diastolic BP ≤ 90 mmHg. At restart, continue at the same dose level 	No modification

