6.6.4 Dose Modification and Toxicity Management of Infusion Reactions Related to Pembrolizumab

Pembrolizumab may cause severe or life-threatening infusion reactions including severe hypersensitivity or anaphylaxis. Signs and symptoms usually develop during or shortly after drug infusion and generally resolve completely within 24 hours of completion of infusion. Dose modification and toxicity management guidelines on pembrolizumab-associated infusion reaction are provided in Table 6–8.

a: If reductions are required resulting in a dose of less than 60 mg QD of regorafenib, then regorafenib will be permanently discontinued.

b: The decision to withhold or permanently discontinue pembrolizumab is at the discretion of the investigator or treating physician. If control achieved or ≤ Grade 2, pembrolizumab may be resumed.

c: Events that require discontinuation include, but are not limited to: Guillain-Barre Syndrome, encephalitis, myelitis, and other clinically important irAEs (eg, vasculitis and sclerosing cholangitis).

Table 6-8: Dose Modification Guidance, Pembrolizumab-associated Infusion Reactions

Event	Regorafenib	Pembrolizumab	Premedication at Subsequent Dosing of Pembrolizumab
Specific guidance f	or PEMBROLIZUMAB-ASSOCIATED INI	USION REACTIONS	
	scitation equipment should be available at nation, refer to CTCAE v 5.0	the bedside and a physician readily available during the	e period of drug administration
G1 Mild reaction; infusion interruption not indicated; intervention not indicated	No modification	Increase monitoring of vital signs as medically indicated until the participant is deemed medically stable in the opinion of the investigator.	None

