G2 Requires therapy or infusion interruption but responds promptly to symptomatic treatment (e.g., antihistamines, NSAIDs, narcotics, IV fluids); prophylactic medications indicated for ≤ 24 hours	No modification	 Stop Infusion Additional appropriate medical therapy may include but is not limited to: IV fluids Antihistamines NSAIDs Acetaminophen Narcotics Increase monitoring of vital signs as medically indicated until the participant is deemed medically stable in the opinion of the investigator. If symptoms resolve within 1 hour of stopping drug infusion, the infusion may be restarted at 50% of the original infusion rate (e.g. from 100 mL/hour to 50 mL/hour). Otherwise dosing will be held until symptoms resolve and the participant should be premedicated for the next scheduled dose. Participants who develop G2 toxicity despite adequate premedication, pembrolizumab 	Participant may be premedicated 1.5h (± 30 minutes) prior to infusion of pembrolizumab with: Diphenhydramine 50 mg p.o. (or equivalent dose of antihistamine). Acetaminophen 500-1000 mg p.o. (or equivalent dose of analgesic).

Table 6-8: Dose Modification Guidance, Pembrolizumab-associated Infusion Reactions

Event	Regorafenib	Pembrolizumab	Premedication at Subsequent Dosing of Pembrolizumab
Specific guidance f	or PEMBROLIZUMAB-ASSOC	NATED INFUSION REACTIONS	
		should be permanently discontinued.	
G3 Prolonged (i.e., not rapidly responsive to symptomatic medication and/or brief interruption of infusion); recurrence of symptoms following initial improvement; hospitalization indicated for other clinical sequelae (e.g., renal impairment, pulmonary infiltrates) G4 Life-threatening; pressor or ventilator support indicated	No modification	Stop Infusion Additional appropriate medical therapy may include but is not limited to: Epinephrine (In cases of anaphylaxis, epinephrine should be used immediately) IV fluids Antihistamines NSAIDs Acetaminophen Narcotics Oxygen Pressors Corticosteroids Increase monitoring of vital signs as medically indicated until the participant is deemed medically stable in the opinion of the investigator. Hospitalization may be indicated. Pembrolizumab should be permanently discontinued. **In cases of anaphylaxis, epinephrine should be used immediately. Participant is permanently discontinued from further study drug treatment	No subsequent dosing

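### After anaphylaxis to pembrolizumab, Section 7.1.1.1 requires withdrawal from study intervention while Table 6-8 leaves regorafenib unchanged, and no text says which prevails

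*Protocol*

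**What the plan says.** Three places in the protocol bear on a participant who has an anaphylactic reaction to a pembrolizumab infusion.

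- **Section 7.1.1.1** lists events after which withdrawal from the study intervention is a MUST. One entry is "Severe allergic reactions, such as exfoliate erythroderma, anaphylaxis, or vascular collapse". It does not say which drug has to have caused the reaction.
- **Section 6.6.4, Table 6-8** gives the guidance for infusion reactions. For the shared Grade 3/4 row, the regorafenib column reads "No modification". The pembrolizumab column stops pembrolizumab permanently and ends with "Participant is permanently discontinued from further study drug treatment".
- **Section 4.1.1.2** states a general rule for the combination: "Treatment with individual drugs (regorafenib or pembrolizumab) may continue on schedule even if the other drug is interrupted or permanently discontinued due to toxicity".

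Withdrawal of one drug alone is handled elsewhere, in Section 7.1.1.2 for regorafenib and Section 7.1.1.3 for pembrolizumab. The introduction to Section 6.6 describes Tables 6-3 to 6-8 as recommendations that support the clinical decision.

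**The concern.** Read literally, the withdrawal criterion and the dose table give opposite instructions on regorafenib for the same participant. A site working from Section 7.1.1.1 ends all study treatment. A site working from Table 6-8, supported by Section 4.1.1.2, stops pembrolizumab and leaves regorafenib as it was. Section 8 allows no protocol waivers, so a site that follows one text departs from the other.

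The main stake is consistent handling of a life-threatening event. The second is reporting: dose modification, including discontinuation, is a secondary safety endpoint in Table 3-1, and the SAP tabulates adverse events leading to discontinuation by drug. How one event is classified would depend on which page the site opened.

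**Working it through.** No arithmetic applies. The check sets the texts side by side.

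**1. Does Table 6-8 cover anaphylaxis?** Yes. Section 6.6.4 opens with "Pembrolizumab may cause severe or life-threatening infusion reactions including severe hypersensitivity or anaphylaxis". The row in question includes "G4 Life-threatening; pressor or ventilator support indicated", and its pembrolizumab column says "In cases of anaphylaxis, epinephrine should be used immediately".

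**2. Does Section 7.1.1.1 cover the same event?** Yes. Anaphylaxis is named and no causative drug is specified, so a reaction to pembrolizumab falls within it.

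**3. Does study intervention in Section 7.1.1.1 mean both drugs?** It reads that way, for four reasons:
- Section 6 defines the term broadly enough to cover any investigational product, then lists regorafenib and pembrolizumab.
- The heading concerns the intervention period as a whole.
- Other entries in the same list, such as death, pregnancy, loss to follow-up and a new anti-cancer therapy, can only end both drugs.
- Single-drug withdrawal has its own two sections. Section 7.1.1.3 already provides for stopping pembrolizumab alone when the Section 6.6 guidance calls for it.

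This is an inference from structure; no sentence says it outright.

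**4. Does any text settle the order?** No. Section 6.6 calls the tables decision support, which might favour the MUST. Section 4.1.1.2 permits the other drug to continue and makes no exception for anaphylaxis. Neither section refers to Section 7.1.1.1, and Section 7.1.1.1 makes no exception for reactions to pembrolizumab.

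**5. What does the last sentence in the row add?** The sentence "Participant is permanently discontinued from further study drug treatment" names no drug. If it means pembrolizumab, it repeats the instruction already in that cell. If it means both drugs, it conflicts with the regorafenib cell beside it. The conflict with Section 7.1.1.1 stands on either reading.

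**6. Which reported counts could move?** SAP Section 5.4.1.2 plans four tables of adverse events leading to discontinuation. The comparison below assumes that each drug's table counts everyone who stopped that drug for the event.

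| SAP table | Section 7.1.1.1 followed | Table 6-8 followed |
|---|---|---|
| Any study intervention | counted | counted |
| Pembrolizumab | counted | counted |
| Regorafenib | counted | not counted |
| Both interventions | counted | not counted |

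Two of the four change. For the participant concerned, the date of last study dose would also differ. That date anchors the end-of-treatment visit (Table 1-1) and the 30-day window for treatment-emergent events (Section 10.3.1).

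**The case against.** The best defence is that the two texts do not have equal force. Section 7.1.1.1 says MUST, the Section 6.6 tables are recommendations, and Section 4.1.1.2 says only that the other drug may continue. A specific mandatory criterion can be taken to limit a general permission. There are also safeguards: Section 8 has immediate safety concerns discussed with the sponsor to decide whether the participant continues, and Section 7.1.1.1 separately requires withdrawal if the investigator judges continuation harmful. This softens the conflict and makes it unlikely that regorafenib would continue without anyone considering the matter. It does not resolve it, because the precedence is never written down and the table's regorafenib entry is unqualified.

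The analysis impact is small, and that part of the defence stands. The action taken is recorded separately for each drug (Section 8.3), tumor assessments are to continue after treatment stops without confirmed radiological progression (Section 8.1), and all treated participants stay in the Full Analysis Set (Section 9.3).

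A reader might be tempted by stronger readings that the documents do not support:
- **That the Table 6-8 row contradicts itself.** The sentence about study drug treatment sits in the pembrolizumab column of a table on pembrolizumab reactions, directly after the instruction to stop pembrolizumab. It is ambiguous, not a proven contradiction.
- **That the same conflict exists for severe exfoliative skin events.** The Table 6-3 skin row lists "rash papular, rash pruritic, exfoliative rash, pruritus" among non-immune skin disorders, and nothing equates such a rash with the erythroderma of Section 7.1.1.1. For confirmed SJS, TEN or DRESS, Table 6-7 permanently stops both drugs, in line with Section 7.1.1.1.
- **That every Grade 3/4 infusion reaction is affected.** Grade 3 in Table 6-8 includes prolonged reactions, recurring symptoms and hospitalization for sequelae, which need not be severe allergic reactions.

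**Conclusion.** The point holds in a limited form. For a Grade 3/4 pembrolizumab infusion reaction that is a severe allergic reaction such as anaphylaxis, Section 7.1.1.1 requires withdrawal from the study intervention, Table 6-8 leaves regorafenib unchanged, Section 4.1.1.2 is compatible with the table, and no text says which governs. The Grade 1 and Grade 2 rows are not involved.

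Few participants would be affected. No headcount is offered: the documents give no rate for such reactions, and the planned 119 participants cannot be taken as the number treated, since the SAP version history records that recruitment stopped early. In the SAP discontinuation tables only the regorafenib and both-interventions counts could shift. The primary endpoint's analysis population is unchanged. The case for correction rests on the gravity of the event and on opposite handling across sites, not on frequency.

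The conclusion assumes that study intervention in Section 7.1.1.1 means both drugs, as its structure indicates, and that the Grade 3 and Grade 4 entries in Table 6-8 share one regorafenib cell, as they do in the text available. It takes no view on which clinical rule is right.

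**What to change.** Reconcile Section 4.1.1.2, Table 6-8 and Section 7.1.1.1:

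1. In Section 7.1.1.1, state whether the severe-allergic-reaction criterion applies to both drugs or only to the causative drug.
2. In the Grade 3/4 row of Table 6-8, name the drug or drugs from which the participant is permanently discontinued.
3. Align the regorafenib column of that row with whatever Section 7.1.1.1 then says, and add a cross-reference in Section 4.1.1.2 if an exception is intended.

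The sponsor decides which rule applies. The cost is a wording change in three places, with no added procedures or data collection. If participants have already had such an event, the study report should say how regorafenib was handled, so that the discontinuation counts can be read correctly.

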7.1.1.2 Withdrawal of Regorafenib only

Participants must be withdrawn from regorafenib for the following reasons:

- Participants who halt therapy for more than 28 consecutive days including the 1-week drug holiday. However, continuation of regorafenib may be considered if, in the investigator's opinion, the participant may continue to benefit from the regorafenib treatment, and after consultation with sponsor.
- Unacceptable toxicity, i.e. an event requiring permanent discontinuation of regorafenib according to dose modification guidance in Section 6.6.

7.1.1.3 Withdrawal of Pembrolizumab only

Participants MAY be withdrawn from pembrolizumab for the following reasons:

• Participants who experience a delay of more than 12 weeks to receive the subsequent pembrolizumab infusion due to treatment-related toxicity or corticosteroids cannot be

Page 78 of 141

reduced to \leq 10 mg prednisone or equivalent per day within 12 weeks, according to dose modification guidance in Section 6.6.

- Unacceptable toxicity, i.e. event requiring permanent discontinuation of pembrolizumab according to dose modification guidance in Section 6.6.
- Discontinuation of pembrolizumab may be considered for participants who have attained a confirmed CR that have been received at least 8 infusions (24 weeks) of pembrolizumab and had at least 2 infusions with pembrolizumab beyond the date when the initial CR was declared.

7.2 Participant Discontinuation/Withdrawal from the Study

A participant must be withdrawn from the study at any time at his/her own request or at the request of their legally acceptable representative (if acceptable by local law).

A participant may be withdrawn from the study at any time at the discretion of the investigator for safety, behavioral, compliance, or administrative reasons. This is expected to be uncommon.

If the participant withdraws consent for disclosure of future information, the sponsor may retain and continue to use any data collected before such a withdrawal of consent.

If a participant withdraws from the study, and additionally requests destruction of her/his samples taken but not yet tested, the investigator must document this (either destruction by site or request to central lab, as applicable) in the site study records.

Withdrawal from active follow-up

Participants MUST be withdrawn from active follow-up if any of the following occurs:

- At their own request or at the request of their legally acceptable representative (if acceptable by local law). At any time during the study and without giving reasons, a participant may decline to participate further. The participant will not suffer any disadvantage as a result.
- Radiologically confirmed PD is observed and/or clinical progression (for participants who discontinued study intervention before PD due to any other reason).
- Start of subsequent systemic anti-cancer treatment.
- Development of a second primary malignancy that requires a different treatment.
- Substantial non-compliance with the requirements of the study.
- If, in the investigator's opinion, continuation of the active visits would be harmful to the participant's well-being.
- Participants lost to follow-up.
- Death.

Participants MAY be withdrawn from active follow-up if any of the following occurs:

• At the specific request of the sponsor and in liaison with the investigator (e.g. obvious non-compliance).

Withdrawal from long-term follow-up

Participants MUST be withdrawn from long-term follow-up if any of the following occurs:

• Withdrawal of consent to long-term follow-up.

Page 79 of 141

- Participants lost to follow-up.
- Death.

Participants MAY be withdrawn from long-term follow-up if any of the following occurs:

• At the specific request of the sponsor and in liaison with the investigator (e.g. obvious non-compliance).

